1. INTRODUCTION

The outline statistical methods to be used for the analysis of trial data are included in the final trial Protocol. This analysis plan provides full details of the results to be presented. Shell data tables were created to provide an overview of the analysis to be conducted by the Data Monitoring and Ethics Committee (see Appendix 1).

2. STUDY SYNOPSIS

A Randomised Placebo Controlled Trial Among Trauma Patients with Significant Haemorrhage of the Effects of Tranexamic Acid on Death and Transfusion Requirement (CRASH-2).

3. STUDY OBJECTIVES

To quantify the effect on death, vascular events and transfusion requirements of the early administration of the antifibrinolytic agent tranexamic acid in patients with trauma and significant bleeding.

3.1. PRIMARY OBJECTIVE

The primary outcome measure is death in hospital within four weeks of injury.

3.2. SECONDARY OBJECTIVES

Secondary outcome measures are:

Blood Products

- Blood products transfusion given
- Number of units of blood products transfused (including the total number of units of red cells, platelets, fresh frozen plasma and cryoprecipitate)

Disability

- Death or dependency: this outcome will be measured using the five point Modified Oxford Handicap Scale. We will dichotomise the scale into 'independent' (no symptoms; minor symptoms; some restriction in lifestyle but independent) and 'dependent' (dependent, but not requiring constant attention; fully dependent; requiring attention day and night; death).

Surgery

- Neurosurgery, chest operation, abdominal operation and pelvis operation. We will analyse all surgery combined and separately.

Thromboembolic episodes

- Stroke, myocardial infarction, pulmonary embolism, clinical evidence of deep vein thrombosis. We will analyse thromboembolic episodes combined and separately.

Gastrointestinal bleeding

Days in intensive care unit

Causes of death will be described to assess whether deaths were due to bleeding, myocardial infarction, stroke, pulmonary embolism, vascular occlusion (bleeding or myocardial infarction or stroke or pulmonary embolism), multi-organ failure, head injury or other.

3.3. ASSESSMENT OF OBJECTIVES

All outcome variables are recorded on the outcome form which is completed entirely from the hospital notes – no extra tests are needed. The outcome form is completed at death, discharge or four weeks post randomisation, whichever occurs first.

3.4. CHANGE OF THE PRIMARY OBJECTIVE DURING THE CONDUCT OF THE STUDY

There has not been any change in the primary outcome of the study. The following secondary outcomes were included: death or dependency, gastrointestinal bleeding, days in intensive care unit, and type of surgical intervention.

4. STUDY DESIGN

4.1 GENERAL DESIGN AND PLAN

A randomised double blind placebo controlled trial. Adults with trauma who are within 8 hours of injury and have either significant haemorrhage, or who are considered to be at risk of significant haemorrhage, are eligible if the responsible doctor is for any reason substantially uncertain whether or not to use an antifibrinolytic agent. Numbered drug or placebo packs will be available in each participating emergency department. Randomisation will involve calling a 24-hour free-call randomisation service. The call should last only a minute or two and at the end of it the randomisation service will specify which numbered treatment pack to use. For hospitals where telephone randomisation is not feasible, randomisation will be by taking the next consecutively numbered treatment pack. No extra tests are required but a short form must be completed one month later or on discharge or on death (whichever occurs first).

4.2 SAMPLE SIZE

Since even a 2% survival advantage for an intervention as simple as TXA would represent a worthwhile benefit, the main trial has been planned to be able to detect a benefit of this size. If the real mortality difference is in fact 20% versus 18%, then there is about an 85% chance that a trial involving 20,000 patients will achieve $2P < 0.01$ (and a 95% chance that it will achieve $2P < 0.05$). With such large numbers, even moderate effects on the numbers needing transfusion or on the mean number of

units transfused will be determined accurately, as will any substantial effects on non-fatal vascular events (haemorrhagic or occlusive).

4.3 RANDOMISATION AND BLINDING

Patients are randomised in one of two ways: Hospitals with reliable telephone access, where the recruiting doctors are able to provide baseline data in English, will use the central telephone randomisation service provided by the Clinical Trial Service Unit (CTSU) in Oxford. During the call, which will last 2-3 minutes, baseline data are collected and recorded on the central computer. To achieve a reasonable balance on the key prognostic factors, the allocation uses a minimisation algorithm balancing for sex, age (16-24 years, 25-34 years, 35 years and older), hours since injury (1 hour or less, 1-3 hours, over 3 hours), type of injury (blunt or penetrating), Glasgow Coma Scale (3, 4-5, 6-8, 9-12, 13-15), Systolic Blood Pressure (>89, 76-89, 50-75, 1-49, 0), Respiratory Rate (>29, 10-29, 6-9, 1-5, 0), Central Capillary Refill Time (2 or less, 3-4, 5 or more) and country, bearing in mind what packs remain at that hospital. The allocated treatment pack number will be given and recorded on the trial entry form. Hospitals in which the doctors feel that central randomisation is not feasible will use a local pack system. At such hospitals, baseline information will be collected on the trial entry form and the next consecutively numbered treatment pack taken from a box of eight packs (with a random allocation sequence based on a block size of eight, also generated by CTSU). Once the pack number is recorded, the patient is included in the trial whether or not the pack was opened or the allocated treatment started.

4.3.1 Blinding

Blinding is achieved through the use of matching placebo. The blinding process is described in Appendix 1.

5. STUDY POPULATIONS

5.1 PARTICIPANT CHARACTERISTICS

A trial profile of participants will be presented as per the CONSORT recommendations (figure 1). The table of baseline characteristics will be as per Table 4 in DMEC shell tables but excluding the components of the GCS.

5.2 DEFINITION OF POPULATIONS FOR ANALYSIS

The analyses will be on an 'intention-to-treat' basis. All patients will be analysed on the basis of the group to which they were randomised, irrespective of whether the patients in the intervention group actually received the intervention.

5.3 MAJOR PROTOCOL DEVIATIONS

These will be described in the results section.

5.4 DEFINITION OF SUB-GROUP POPULATIONS

Analysis of the primary outcome will be stratified on:

- hours from injury to randomisation and the initiation of treatment (less than one hour, one to three hours, more than three hours)
- severity of haemorrhage as assessed by systolic blood pressure (≤ 75 , 76-89, > 89 mmHg)
- Glasgow Coma Scale (severe [GCS 3-8], moderate [GCS 9-12], mild [GCS 13-15])
- type of injury (blunt/blunt & penetrating, or penetrating only)

Subsequent analyses will include subgroup analyses according to baseline risk of mortality. We will develop a prognostic model including all the baseline variables (age, sex, systolic blood pressure, heart rate, respiratory rate, Glasgow Coma Score, number of hours since injury, central capillary refill time and type of injury). This model will be derived only from the control group. We will categorise the patients according to tertiles of risk and we will report the relative and absolute measures of effect for each category.

6. STATISTICAL ANALYSIS

6.1 GENERAL

For each binary outcome we will report relative risks with 95% confidence intervals and give a two-sided p-value for statistical significance. For analysis of the pre-specified subgroups (primary outcome only) we will report relative risks with 99% confidence intervals with two-sided p-value.

6.2 POOLING OF SITES

The data will be pooled across all participating sites.

6.3 INTERIM ANALYSES

Interim analyses were conducted by the independent DMEC as per the DMEC SOP.

6.4 TIME-POINTS FOR ANALYSIS

There will be one analysis at the end of the trial after the database has been locked.

6.5 METHODS FOR HANDLING MISSING DATA

A complete case analysis will be conducted (i.e. only including cases for which the relevant outcome data are available). There will be no imputation for missing data.

6.6 STATISTICAL ANALYTICAL ISSUES

6.6.1 Adjustments for covariate

There will be no covariate adjustment in the primary analysis.

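### The unadjusted primary analysis is valid and reaches its stated power, but it gives up precision that adjustment for the minimisation factors would recover at low cost

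*SAP*

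**What the plan says.** Section 6.6.1 is a single sentence: "There will be no covariate adjustment in the primary analysis". Section 6.2 adds that "The data will be pooled across all participating sites". The outcome is binary (section 3.1: "The primary outcome measure is death in hospital within four weeks of injury"), and the analysis in sections 6.1 and 9.2.1 is an unadjusted comparison: "For each binary outcome we will report relative risks with 95% confidence intervals and give a two-sided p-value for statistical significance".

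Section 4.3 describes two allocation routes. At hospitals using the telephone service, "To achieve a reasonable balance on the key prognostic factors, the allocation uses a minimisation algorithm balancing for sex, age", hours since injury, type of injury, Glasgow Coma Scale, systolic blood pressure, respiratory rate, capillary refill time and country. Elsewhere the next pack is taken from a box with a random block size of eight, with no balancing on patient characteristics. Baseline data are recorded on both routes. The split of patients between them is not stated.

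The only modelling of baseline variables is in section 5.4, where a prognostic model from the control group forms risk tertiles for a later subgroup analysis. Section 6.6.1 does not bar a supportive adjusted analysis, but none is specified anywhere.

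**The concern.** The SAP regards these factors as important enough to govern allocation and then leaves them out of the analysis without giving a reason. Two separate consequences follow.

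- **Precision, for all patients.** A baseline factor that predicts death explains part of the outcome variance however the patient was allocated. An unadjusted relative risk leaves that variance in its standard error.
- **Calibration, for minimised patients only.** Balancing a prognostic factor by design reduces the true sampling variance of the treatment contrast. The unadjusted standard error does not reflect this, so the interval covers somewhat more often than 95% and the test rejects somewhat less often than 5% under the null.

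At stake is the width of the interval for the main result, and power at the stricter of the two significance levels in section 4.2. Section 6.6.3 also makes the overall relative risk the preferred guide for every subgroup unless heterogeneity reaches p < 0.001, so much rests on the precision of that one estimate.

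**Working it through.** **Inputs from the SAP.** Mortality 20% versus 18%, 20,000 patients and two-sided levels 0.01 and 0.05 (section 4.2); 1:1 allocation (four of each in a block of eight, in the blinding appendix). **Assumption.** R², the share of variance in the binary outcome explained by the adjustment factors, is not given. The range used is 0.10 / 0.20 / 0.30.

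**1. Reproduce the stated power.** Section 4.2 says "there is about an 85% chance that a trial involving 20,000 patients will achieve" 2P < 0.01, and gives "a 95% chance that it will achieve" 2P < 0.05.

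SE = √(0.20×0.80/10,000 + 0.18×0.82/10,000) = 0.005546, so z = 0.02/0.005546 = 3.606.

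- Level 0.01: Φ(3.606 − 2.576) = 84.9% (84.8% with the pooled variance under the null).
- Level 0.05: Φ(3.606 − 1.960) = 95.0%.

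Both figures reproduce as an unadjusted test.

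**2. Interval width.** At a relative risk of 0.90, SE(log RR) = √(0.82/1,800 + 0.80/2,000) = 0.02925. The half-width is 1.96 × 0.02925 = 0.0573, and the unadjusted 95% interval is 0.850 to 0.953. Adjustment multiplies the half-width by √(1 − R²).

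**3. Power.** Two baselines are needed, because close balance also helps the unadjusted test. With c = 2.576 or 1.960:

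- adjusted: Φ(3.606/√(1−R²) − c)
- unadjusted, simple randomisation: Φ(3.606 − c)
- unadjusted, near-perfect balance: Φ((3.606 − c)/√(1−R²))

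**4. True size of the nominal 5% unadjusted test.** With all patients minimised to near-perfect balance, it is 2Φ(−1.96/√(1−R²)). With half minimised (an assumption), it is 2Φ(−1.96/√(1−0.5R²)).

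| Assumed R² | 0.10 | 0.20 | 0.30 |
|---|---|---|---|
| Width ratio √(1−R²) | 0.949 | 0.894 | 0.837 |
| Adjusted 95% interval at RR 0.90 | 0.852–0.950 | 0.855–0.947 | 0.858–0.944 |
| Adjusted power, 0.01 | 89.0% | 92.7% | 95.9% |
| Unadjusted, 0.01, simple | 84.9% | 84.9% | 84.9% |
| Unadjusted, 0.01, near-perfect balance | 86.1% | 87.5% | 89.1% |
| Gain at 0.01 (points), balanced to simple | 3 to 4 | 5 to 8 | 7 to 11 |
| Adjusted power, 0.05 | 96.7% | 98.1% | 99.1% |
| Unadjusted, 0.05, simple | 95.0% | 95.0% | 95.0% |
| Unadjusted, 0.05, near-perfect balance | 95.9% | 96.7% | 97.5% |
| Gain at 0.05 (points), balanced to simple | 1 to 2 | 1 to 3 | 2 to 4 |
| True size, all minimised (bound) | 3.9% | 2.8% | 1.9% |
| True size, half minimised | 4.4% | 3.9% | 3.4% |

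**5. Check by simulation.** Trials of 20,000 patients (1,500 per setting) compared the unadjusted log relative risk with one standardised from a logistic model. The assumed discrimination (AUC) was 0.75 / 0.82 / 0.87, which corresponds to R² of about 0.13 / 0.24 / 0.34. The adjusted standard error was 0.93 / 0.87 / 0.81 of the unadjusted one. Coverage of the unadjusted 95% interval was 95.0% / 95.1% / 95.6% under simple randomisation and 96.2% / 97.8% / 98.8% under close balance. Adjusted coverage stayed between 94.5% and 95.5% in all settings. Monte Carlo error is about √(0.95×0.05/1,500) = 0.6 points, so the simulation agrees with the formulas.

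**The case against.** The strongest reply is that nothing in the SAP is wrong here. The unadjusted analysis was chosen in advance, the sample size was built for it, the stated power reproduces, and any miscalibration is conservative: no bias and no inflation of type I error. In a trial of 20,000 patients, simplicity is a defensible reason to leave the analysis unadjusted. All of that stands, and it makes this a matter of efficiency.

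Several further points limit the size.

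- A reader might infer that the interval is too wide for the trial as a whole. Section 4.3 does not support that. Local-pack patients are not balanced on these factors, so for them the unadjusted interval has essentially nominal coverage, though it is still less precise than it could be.
- Even by telephone, minimisation aims only at reasonable balance over coarse bands (everyone aged 35 or older is in one band) and takes account of the packs left at the hospital. The 3.9% / 2.8% / 1.9% sizes are therefore a bound.
- A reader might add the full power gain from 85% to the full loss of size. The first assumes simple randomisation and the second near-perfect balance, so they cannot both hold.
- The SAP calls the factors key but gives no measure of their strength. Any statement that they are strongly prognostic is an assumption.
- The improvement is not free. Notes 3 and 4 to the SAP's tables show that systolic pressure and respiratory rate can be unknown, and countries with few deaths need a rule.

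These points shrink the gain but do not remove it. The precision loss does not depend on the allocation route, and the SAP offers no reason for accepting it.

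**Conclusion.** The point holds as a loss of efficiency. It does not show an invalid analysis or an underpowered trial: the SAP delivers its stated 85% and 95% as written.

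Under the assumed R² of 0.10 to 0.30, a marginal relative risk adjusted for the minimisation factors would have an interval about 5% to 16% narrower. It would gain about 3 to 11 points of power at two-sided 0.01 and about 1 to 4 at 0.05. The lower end of each gain belongs to weak factors and close balance, the upper end to strong factors and simple randomisation. The conservatism of the unadjusted interval is confined to minimised patients and is mild: if half were minimised, the nominal 5% test would have a true size of about 4.4% to 3.4%.

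The direction is secure. The size rests on R² and on the telephone share, and the SAP states neither.

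**What to change.** Before database lock, amend section 6.6.1 as follows.

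- The primary result is a marginal relative risk with a 95% confidence interval and two-sided p-value, from one named method: logistic regression with standardisation over all analysed patients. This keeps the effect measure of sections 6.1 and 9.2.1; a conditional odds ratio would not. Name the variance estimator as well.
- The covariates are the factors listed in section 4.3: sex, age, hours since injury, type of injury, Glasgow Coma Scale, systolic pressure, respiratory rate, capillary refill time and country. State how each is coded.
- Unknown baseline values form their own category, so that no patient is dropped for a missing covariate.
- A stated rule, fixed without reference to treatment arm, pools countries with few deaths.
- The unadjusted relative risk is reported alongside.

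The cost is some SAP wording, slightly more analysis code and a model that must be fixed in advance. No new data are needed.

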6.6.2 Multiple Comparisons

There will be no adjustment for multiple comparisons. We will report 99% confidence intervals for subgroup analyses of the primary outcome.

6.6.3 Examination of Subgroups

We will report relative risks with 99% confidence intervals for the primary outcome by the following subgroups:

- hours from injury
- severity of haemorrhage systolic blood pressure (≤ 75 , 76-89, >89 mmHg)
- Glasgow Coma Scale (severe, moderate, mild)
- type of injury (blunt, blunt & penetrating, or penetrating only)

We will conduct a test of homogeneity of effects across the subgroups and report a p-value. Unless there is strong evidence against the null hypothesis of homogeneity of effects (i.e. $p < 0.001$) the overall relative risk will be considered as the most reliable guide to the approximate relative risks in all subgroups.

7. EVALUATION OF DEMOGRAPHICS AND BASELINE CHARACTERISTICS

7.1 DEMOGRAPHICS AND BASELINE CHARACTERISTICS

As outlined above, a trial profile will be presented as per the CONSORT recommendations (figure 1). The baseline characteristics will be presented according to treatment (table 1).

8. EVALUATION OF TREATMENT COMPLIANCE AND EXPOSURE

8.1 COMPLIANCE TO STUDY DRUG AND TREATMENT

Compliance with study treatment will be defined as:

- Received allocated intervention (loading dose)
- Known not to have received allocated intervention (loading dose)
- Unknown whether received allocated intervention (loading dose)

- Continued allocated intervention (maintenance dose)
- Known not to have continued allocated intervention (maintenance dose)
- Unknown whether continued allocated intervention (maintenance dose)

This will be reported in figure 1.

9. EVALUATION OF PARAMETERS

9.1 ANALYSIS OF PRIMARY, SECONDARY AND OTHER EFFICACY ENDPOINTS

See section 6 above.

9.2 METHOD FOR ANALYSIS OF EFFICACY ENDPOINTS

9.2.1 Binary Data

For each binary outcome we will report relative risks with 95% confidence intervals and give a two-sided p-value for statistical significance. For analysis of the pre-specified subgroups (primary outcome only) we will report relative risks with 99% confidence intervals with two-sided p-value.

9.2.2 Count Data

Means and standard deviations will be estimated for count outcomes. We will report the two-sided p-value for statistical significance of the difference in means of logarithms of count outcomes.

9.2.3 Time-to-Event Data

There will be no analysis of time to event data.

9.2.4 Ordinal Scales and Non-Ordered Scales Data

For the analysis of the patients' condition at discharge, the five point scale will be dichotomised into independent (no symptoms, minor symptoms, and some restriction in lifestyle but independent) and dependent (including death) categories.

10. EVALUATION OF SAFETY PARAMETERS

10.1 ADVERSE EVENTS

Numbers and type will be described using MedDRA codes (Version 12.1).

FIGURE 1 – CONSORT FLOW OF PATIENTS

[figure not shown]

TABLE 1 – BASELINE DATA - ALL PATIENTS RANDOMIZED

Percentages are of group total unless specified		TXA	Placebo
Patients randomized as of <Date>			
Gender²	Male		
	Female		
Age²	Mean age in years (SD)		
	<25 years		
	25-34 years		
	35-44 years		
	≥45 years		
Hours since injury²	<1 hour		
	1-3 hours		
	>3 hours		
Type of injury²	Blunt†		
	Penetrating		
Systolic BP (mmHg)²	≥90 mmHg SBP		
	76-89 mmHg SBP		
	≤75 mmHg SBP		
Respiratory rate (per min)²	≥30		
	10-29		
	6-9		
	<6 ⁴		
Central capillary refill time (secs)²	2 or less		
	3 to 4		
	5 or more		
Heart rate (per min)²	>107		
	92-107		
	77-91		
	<77		
Glasgow Coma Score²	Median [IQR]		
	Severe (GCS 3-8)		
	Moderate (GCS 9-12)		
	Mild (GCS 13-15)		

† Blunt/ Blunt & penetrating

TABLE 2. DEATH WITHIN 4 WEEKS - ALL PATIENTS RANDOMIZED

		TXA	Placebo	RR (95% CI)	p-value
All patients					
Pre-specified subgroups				RR (99% CI)	p-value
(i) Severity of haemorrhage	≥90 mmHg SBP				
	76-89 mmHg SBP				
	≤75 mmHg SBP				
(ii) Time since injury	<1 hour				
	1-3 hours				
	>3 hours				
(iii) Glasgow Coma Scale	Severe (GCS 3-8)				
	Moderate (GCS 9-12)				
	Mild (GCS 13-15)				
(iv) Type of injury	Blunt*				
	Penetrating only				

* Blunt/ Blunt & penetrating

Analysis will include p-value from test of homogeneity of effects between subgroups

TABLE 3 BLOOD PRODUCTS† TRANSFUSION GIVEN

		TXA	Placebo	RR (95% CI)	p-value
All patients					

†All types of blood products (including red cells, fresh frozen plasma, platelets and cryoprecipitate)

TABLE 4 DISTRIBUTION OF NUMBER OF BLOOD UNITS

	TXA	Placebo	Mean difference (95% CI)‡	p-value
Mean units transfused [SD]				

‡Analysis will use logarithmic transformation of number of units transfused

TABLE 5. DEATH OR DEPENDENCY AT 4 WEEKS, DISCHARGE, OR TRANSFER

		TXA	Placebo	RR (95% CI)	p-value
All patients					

TABLE 6 MANAGEMENT AND COMPLICATIONS

		TXA	Placebo	RR (95% CI)	p-value
All surgery					
	NS operation				
	Chest operation				
	Abdominal operation				
	Pelvis operation				
Thromboembolic episodes					
	Pulmonary embolism				
	Deep vein thrombosis				
	Stroke				
	Myocardial infarction				
Gastrointestinal bleeding					
Days in intensive care unit				Mean difference (95% CI)‡	p-value
Mean days in ICU [SD]					

‡Analysis will use logarithmic transformation of number of days in ICU

TABLE 7. CAUSE OF DEATH

		TXA	Placebo	RR (95% CI)	p-value
Bleeding					
Vascular occlusion					
	Myocardial infarction				
	Stroke				
	Pulmonary embolism				
Multi organ failure					
Head injury					
Other					

Notes

1. All analyses include all patients randomized, on an intention-to-treat basis
 2. Groups are pre-specified randomization strata
 3. Includes patients for whom Systolic BP was not known
 4. Includes patients for whom respiratory rate was not known
 5. Denominators are of patients with management data received; numerators are number of patients non-compliant
 6. Denominators are of patients with information on dose received
- * indicates $|z| > 3$

Crash 2 : Blinding of placebo/active products

The study requires the test drug Tranexamic Acid and placebo (Sodium Chloride 0.9%) be supplied in ampoules and packaging which are blinded i.e. are of identical appearance whilst still permitting rapid identification in an emergency.

Tranexamic Acid (Cyklokapron brand) ampoules:

The product is supplied in clear glass 5ml ampoules with paper label and coloured neck rings of green and yellow. All label text is printed onto the paper label.

The blinding process is the complete removal of the original manufacturers label and its replacement with the clinical study label bearing patient/pack randomisation number and text in compliance with requirements for investigational medicinal products in the EU.

Placebo (Sodium Chloride 0.9%) ampoules

The placebo is supplied in identical clear glass ampoules with coloured neck rings of green and yellow. Care is taken during the production process to ensure that ampoules are filled to the same height and sealed to the same height as the Tranexamic acid.

Ampoules can be identified by using the unique randomisation code printed onto the label. This number enables access to the audit trail to trace the full history of the product

Ampoules are packed into patient treatment cartons which also contain an empty syringe, needle and 100ml saline for infusion. Quality assurance procedures ensure that cartons and other components used for both active and placebo containing packs are of similar appearance in order to preserve the blind. Pack identification is provided by the randomisation code printed onto labels fixed directly to the carton.

Patient packs containing Tranexamic acid and also those containing placebo are packed in balanced blocks of 8 (4 Tranexamic Acid: 4 placebo) into an Investigator Supply Box. The fixed numerical sequence of patient packs in the box is in random order of identity. The box is labelled with a unique box number that relates to the Patient Packs it contains.

All processes are carried with strict adherence to good manufacturing procedures for investigational medicinal products.

[name] B.Pharm.,MRPharmS
Technical Director
EU Qualified Person
9 March 2005
